## **Cohort B**

To evaluate the primary endpoint of objective response rate per iRECIST at 12 weeks with a null hypothesis of an objective response rate (ORR) of 13.3% and an alternative hypothesis of an ORR of 29%, 30 patients in a two-stage design will be enrolled, with 15 patients in the first stage and 15 patients in the second stage. At the first stage analysis, if at least 2 responses are observed out of 15 patients, the study may continue through the second stage. At the second stage analysis, if at least 7 responses are observed out of the total 30 patients, the null hypothesis will be rejected and further research considered warranted. The overall power for objective response rate at 12 weeks is 80.1%. The overall type I error, the chance of incorrectly rejecting the null hypothesis is 9.2% (targeted alpha of 0.10). The probability of stopping at the first stage under the null hypothesis is 38.8%. The operating characteristics of this design are calculated using the exact binomial distribution.

## **3. GENERAL ANALYSIS CONVENTION**

### **3.1 General Methods**

All summaries will be presented separately for each cohort, and overall for all subjects combined.

For continuous variables, descriptive statistics (number (n), mean, median, standard deviation, minimum and maximum) will be presented. For categorical variables, frequencies and percentages will be presented.

For time-to-event variables, 25th, 50th (median) and 75th percentile will be estimated using the Kaplan-Meier method. Number of patients with event and number of patients censored will be presented. As appropriate, a 95% CI will be presented. Graphical displays will also be presented, as appropriate.

All data collected will be presented in by-patient data listings

### **3.2 Trial Periods**

The pre screening period is up to 28 days prior to first drug administration. Patients will undergo tumor assessments every 6 weeks ( $\pm 7$  days) until approximately 12 months following first dose of study treatment, or earlier if clinically indicated. After 12 months, tumor assessments will be required every 12 weeks ( $\pm 7$  days). Survival follow-up information will be collected via telephone calls, patient medical records, and/or clinical visits approximately every 3 months for up to 3 years, until death, lost to follow-up, withdrawal of consent, or trial termination by Sponsor. The Trial Schedule of Events is presented in Appendix A.

Sponsor: Sensi Biotherapeutics

Protocol: SNS301-2-2

### 3.3 Visit Windows

The allowed visit windows are summarized in Table 1 below:

Parameter	Visit	Allowed Window
Tumor Biopsy	Week 6	± 3 days
SNS-301 Administration (When pembrolizumab is given every three weeks)	Day 0, Week 3, 6, 9, 15, 21, 27, 33, 39 and 45	± 3 days
	After week 45, every 12 weeks until confirmed disease progression, unacceptable toxicity, deemed intolerable by the investigator or up to 24 months in patients without disease progression.	± 3 days
SNS-301 Administration (When pembrolizumab is given every six weeks)	Day 0, Week 3, 6, 12, 18, 24, 30, 36, 42 and 48	± 3 days
	After Week 48, every 12 weeks until confirmed disease progression, unacceptable toxicity, deemed intolerable by the investigator or up to 24 months in patients without disease progression.	± 3 days
Pembrolizumab Administration	Every 3 weeks until confirmed disease progression, unacceptable toxicity, deemed intolerable by investigator or up to 24 months in patients without disease progression	± 3 days
Imaging	Week 6	± 7 days
	Every 6 Weeks till Week 54	± 7 days
	Every 12 Weeks after Week 54	± 7 days
Vital Signs (Heart rate, respiratory rate, blood pressure, and temperature)	15 Min after start of first infusion	± 5 Min
	30 Min after start of first infusion	± 5 Min
	45 Min after start of first infusion	± 5 Min

Sponsor: Sensi Biotherapeutics

Protocol: SNS301-2-2

	60 Min after start of first infusion	± 5 Min
	30 Min after first infusion	± 10 Min
	60 Min before subsequent infusions	<60 Min to infusion
	30 Min after subsequent infusions	± 5 Min

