4. SNS-301 will be administered intradermally using the 3M micro-needle device. The dosing schedule will be as follows: Day 0, Week 3, Week 6, Week 9 then every 6 weeks (\pm 3 days) for 6 additional doses, thereafter every 12 weeks (\pm 3 days) until confirmed disease progression, unacceptable toxicity, deemed intolerable by the investigator or up to 24 months in patients without disease progression.
5. Pembrolizumab will be administered either every 3 weeks or every 6 weeks until confirmed disease progression, unacceptable toxicity, deemed intolerable by the investigator or up to 24 months in patients without disease progression.
6. Imaging will be performed at 6 weeks (\pm 7 days) calculated from the first dose and will continue to be performed every 6 weeks (\pm 7 days), for the first 54 weeks, or earlier if clinically indicated. Thereafter, imaging will be performed approximately every 12 weeks (\pm 7 days). Imaging timing should follow calendar days and should not be adjusted for delays or changes in treatment administration dates.
7. In patients who discontinue trial therapy for any reason other than radiologically defined confirmed progression, tumor imaging should be performed at the time of treatment discontinuation (\pm 4 weeks). If previous tumor imaging was obtained within 4 weeks prior to the date of discontinuation, then additional tumor imaging at treatment discontinuation is not required.
8. Patients will be followed for all adverse events (AEs) for 30 days and for adverse events of special interest (AESI) and serious adverse events (SAEs) occurring up until 90 days after the last dose of study treatment or until the start of a new anti-cancer treatment, whichever comes first. If the investigator becomes aware of an AESI or SAE that is considered related to study treatment after discontinuation from the trial, those events should be reported to the Sponsor within 24 hours.
9. All patients who experience disease progression, have unacceptable toxicity or start a new anti-cancer therapy and are discontinued from the trial will be followed for survival and subsequent anti-cancer therapy. Patients should be contacted (i.e. by telephone) every 3 months to assess for survival status for up to 3 years, until death or patient withdraws consent. A pregnancy test is also required for WOCBP every 3 months.

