RECIST/iRECIST	X	Q6w from Day 0 until ~12 months, there after Q12w							
Hematology^m	X	X ^f	X ^f	X ^f	X ^f	X ^f		X	
Serum Chemistryⁿ	X	X ^f	X ^f	X ^f	X ^f	X ^f		X	
Coagulation Panel (aPTT, INR)	X								
Urinalysis^o	X			X		X		X	
Pregnancy^p	X	X	X	X	X	X		X	X
TSH, T3 and Free T4^q	X			X		X			
CPK	X							X	
HPV/EBV, if unknown	X								
PDL-1	X								
Blood samples for immunology assessments^r		X	X	X	X	At week 12, then Q6 weeks until Week 36 and Q12w thereafter as well as at disease progression			
Tumor specimens^s	X			X		Up to 2 optional biopsies and at disease progression			
Adverse Events^t	X	X	X	X	X	X		X	X
Pembrolizumab^u		X		X		X			

SNS-301 ^v		X	X	X	X	After week 12, Q6w for 6 more doses (week 45), thereafter Q12w until PD or 24 months if no PD		
Survival and new anti-cancer therapy follow-up ^w								X

Note: Assessments scheduled on the days of study treatment should be performed before the study treatment unless otherwise noted.

^a Written informed consent can be obtained up to 28 days prior to Day 0 and is required for performing any trial-specific tests or procedures. However, tumor tissue collection (archived or fresh) can exceed 28 days to ensure that sufficient time is available for obtaining the requested sample for trial purposes. Additionally, a pre-screening informed consent is available to obtain archived tumor tissue prior to the study's primary consent. Results of standard-of-care tests or examinations performed prior to obtaining informed consent and within 28 days prior to Day 0 may be used for screening assessments rather than repeating such tests. Screening labs (CBC and chemistry) may be used for Day 0 if they are within 10 days of Day 0.

^b Patients who discontinue early from study treatment (i.e., progression, adverse event, etc.), will be asked to return to the clinic within 30 days after the last dose for a treatment discontinuation visit.

^c Cancer history includes stage, date of diagnosis, and prior anti-tumor treatment. Previous progression data should be collected as well. Demographic information includes sex, age, and self-reported race/ethnicity. HPV, EBV, reproductive status and smoking/alcohol history should also be captured.

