^t AEs will be collected from the time of informed consent until 30 days after the last dose of study treatment or until initiation of another anti-cancer therapy, whichever occurs first. SAEs and AESIs will be collected from the time of informed consent until 90 days after the last dose of study treatment or until initiation of anti-cancer therapy, whichever occurs first.

^u Pembrolizumab will be given every 6 weeks until confirmed disease progression, unacceptable toxicity, deemed intolerable by investigator or up to 24 months in patients without disease progression. **After week 9, the pembrolizumab and SNS-301 visits will not coincide. The SNS-301 dosing should not be adjusted. The investigator may choose to give a 3-week dose (i.e., pembrolizumab 200 mg) in order for the visits to align. The investigator should consult the sponsor if there are questions regarding aligning the study treatment schedule.** The window for each visit is \pm 3 days unless otherwise noted. A 60 minute observation period is recommended for the first dose and 30 minutes for subsequent doses.

^v SNS-301 is administered Day 0, Week 3, Week 6 and Week 9, then every 6 weeks for 6 more doses (until week 48). Thereafter it will be administered every 12 weeks until confirmed disease progression, unacceptable toxicity, deemed intolerable by investigator or up to 24 months in patients without disease progression. The window for each visit is \pm 3 days unless otherwise noted. A 30-minute observation period is recommended after each study treatment.

^w Survival follow-up information will be collected via telephone calls, patient medical records, and/or clinical visits approximately every 3 months for up to 3 years, until death, lost to follow-up, withdrawal of consent, or trial termination by Sponsor. All patients will be followed for survival and new anticancer therapy information unless the patient requests to be withdrawn from follow-up; this request must be documented in the source documents and signed by the investigator. If the patient discontinues study treatment without documented clinical disease progression, every effort should be made to follow up regarding survival, progression and new anti-cancer therapy.

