The pembrolizumab dose of 200 mg dose IV infusion over 30 minutes every three weeks or pembrolizumab dose of 400 mg IV infusion over 30 minutes every six weeks has been chosen based on the US package insert for this indication. As of April 2020, Merck has extended dosing for all approved indications to allow for three or six week dosing. SNS-301 (1×10^{11} particles in 1ml ID injection) is planned to be administered when pembrolizumab dosing is every 3 weeks. SNS-301 will be given at Day 0, Week 3, Week 6, Week 9, then every 6 weeks for 6 more doses (45 weeks). Thereafter, SNS-301 is to be administered every 12 weeks until confirmed disease progression, unacceptable toxicity, or deemed intolerable by the investigator. When pembrolizumab dosing is every 6 weeks SNS-301 dosing will be at Day 0, Week 3, Week 6, Week 12, every 3 weeks for 4 doses (12

weeks), and then every 6 weeks for 6 more doses (45 weeks). Thereafter, SNS-301 is to be administered every 12 weeks until confirmed disease progression, unacceptable toxicity, or deemed intolerable by the investigator.

The SNS-301 dose was chosen based on the safety, immunogenicity and preliminary efficacy data that were available from the Phase 1 dose escalation study (Study SNS0216) conducted in patients with biochemically relapsed prostate cancer. The overall safety profile, SNS-301 was considered to be tolerable with no dose limiting toxicities (DLTs) observed and no discernable safety differences.

The immunogenicity of SNS-301 was evaluated for both antibody and cellular responses. At all dose levels tested, SNS-301 was able to generate specific anti-ASPH responses, however, the mid-dose level (and proposed Phase 2 clinical dose) demonstrated the best ASPH-specific antibody and cellular responses.

The Sponsor evaluated the clinical efficacy of SNS-301 by examining PSA kinetics such as the effect of SNS-301 on PSA doubling time (PSADT), absolute PSA levels and PSA velocity (PSAV). A positive effect in lengthening the time in months to double the PSA value in the treatment phase compared to the pre-treatment phase was observed in 2 of 3 patients in both the low dose (2×10^{10} particles) and the mid dose (1×10^{11} particles) treatment groups. In the high dose (3×10^{11} particles) group, 3 of 6 patients showed a positive treatment effect.

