The study treatment will be administered only to patients included in this study following the procedures set out in this clinical study protocol. Administration of the study treatment will be supervised by the Investigator or sub-Investigator. Details of the exact time of administration of medication (day/month/year, hour:minute) will also be documented in the eCRF.

7.1.2.1 *SNS-301 Dosing*

The vaccine will be delivered intra-dermally by a single-use 3M® hollow microstructured transdermal system (hMTS) device. Patients will be administered intradermally the SNS-301 dose of 1.0×10^{11} particles in 1 mL per administration.

Patients will receive SNS-301 on a staged schedule starting every three weeks for four doses, every six weeks for 6 doses and thereafter every twelve weeks.

When pembrolizumab and SNS-301 are dosed on the same day, SNS-301 will be dosed approximately 1 hour after IV infusion of pembrolizumab for the first dose. Subsequent doses of SNS-301 and pembrolizumab can be dosed in any order.

A 60 minutes observation period is recommended for the first dose on this study and 30 minutes for subsequent doses.

Additional information on Dosing, Administration and Preparation can be found in the pharmacy manual for SNS-301.

7.1.2.2 *Pembrolizumab Dosing*

A fixed dose of 200 mg pembrolizumab as an intravenous infusion over 30 minutes every 3 weeks or a fixed dose of 400 mg pembrolizumab, as an intravenous infusion over 30 minutes every 6 weeks will be administered.

A sterile, non-pyrogenic, low-protein binding 0.2 micron to micron in-line or add-on filter will be utilized. Do not co-administer other drugs through the same infusion line.

A 60 minutes observation period is recommended for the first dose on this study and 30 minutes for subsequent doses.

Additional information of Dosing, Administration and Preparation can be found in the package insert for Keytruda https://www.merck.com/product/usa/pi_circulars/k/keytruda/keytruda_pi.pdf

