## 2.3 Treatments and Assignment to Treatments

### SNS-301 Dosing

- SNS-301 ( $1 \times 10^{11}$  dose/1ml) ID is administered using the 3M® hollow microstructured transdermal system (hMTS) device.
- Patients will receive SNS-301 on a staged schedule starting every three weeks for four doses, every six weeks for 6 doses and thereafter every twelve weeks.
- When pembrolizumab and SNS-301 are dosed on the same day, SNS-301 will be dosed approximately 1 hour after IV infusion of pembrolizumab for the first dose. Subsequent doses of SNS-301 and pembrolizumab can be dosed in any order.
- A 60 minutes observation period is recommended for the first dose on this study and 30 minutes for subsequent doses.

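### For six-weekly pembrolizumab, SAP Table 1 contradicts the protocol's single SNS-301 regimen, and the protocol's anticoagulant-level row, on its natural reading, misses every SNS-301 dose after Week 9

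*SAP*

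**What the plan says.** The governing regimen is stated once for all patients. The protocol synopsis gives "Day 0, Week 3, Week 6, Week 9 then every 6 weeks" for six further doses, then 12-weekly dosing. Protocol 7.1.2.1 describes "a staged schedule starting every three weeks for four doses, every six weeks for 6 doses and thereafter every twelve weeks", and SAP 2.3 repeats it. Footnote u of the six-weekly pembrolizumab schedule makes the intent explicit: "After week 9, the pembrolizumab and SNS-301 visits will not coincide. The SNS-301 dosing should not be adjusted".

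Other current text for six-weekly pembrolizumab differs:

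- **SAP 3.3, Table 1:** SNS-301 at "Day 0, Week 3, 6, 12, 18, 24, 30, 36, 42 and 48". The only pembrolizumab window listed is three-weekly, although SAP 2.3 allows six-weekly dosing.
- **Six-weekly schedule, footnote v:** "SNS-301 is administered Day 0, Week 3, Week 6 and Week 9, then every 6 weeks for 6 more doses (until week 48".
- **Six-weekly schedule, SNS-301 row:** a dose is marked at Week 9, followed by "After week 12, Q6w for 6 more doses (week 45), thereafter Q12w until PD or 24 months if no PD".
- **Protocol 3.2.3:** "When pembrolizumab dosing is every 6 weeks SNS-301 dosing will be at Day 0, Week 3, Week 6, Week 12". The same sentence goes on to describe four three-weekly doses and a six-weekly phase ending at 45 weeks.

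For patients on anticoagulants, protocol 9.2.14.4 requires a drug or factor Xa level at baseline, at every SNS-301 dose and at the end-of-study visit. In the six-weekly schedule the anticoagulant row marks screening, Day 0 and Weeks 3, 6 and 9. After Week 12 it goes six-weekly to Week 42, then 12-weekly.

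**The concern.** Section 9 of the protocol sends sites to the schedule tables for the procedures due at each visit. If a table and the governing text give different weeks, a site can follow the table in good faith and still depart from the protocol.

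The anticoagulant row matters most. Protocol 9.3.11 says SNS-301 may disturb coagulation because its target modifies clotting and anticoagulant proteins, and 9.2.14.4 asks for the levels in order to check that they stay in therapeutic range. Levels drawn midway between doses are not the ones 9.2.14.4 asks for.

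In the SAP, a dose given exactly per protocol would fall outside the window Table 1 lists, while an off-protocol dose at Week 12 would fall inside one.

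**Working it through.** **Inputs.** Lead-in doses at Weeks 0, 3, 6 and 9, then six six-weekly doses, then 12-weekly (synopsis, 7.1.2.1, SAP 2.3). Dosing window of 3 days either side (SAP Table 1). Treatment for up to 24 months, taken here as 104 weeks (an assumption).

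**1. End of the six-weekly phase.** Footnote v prints Week 48. From its own inputs the end is 9 + 6 × 6 = 45, so 48 is not reproduced. It follows only from a Week 12 start: 12 + 36 = 48. The six doses still fall at 15, 21, 27, 33, 39 and 45, so the printed 48 moves none of them. If a site counted the 12-weekly phase from Week 48, those doses would fall at 60, 72, 84 and 96 instead of 57, 69, 81 and 93, each three weeks late.

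**2. Full regimen.** 0, 3, 6, 9, 15, 21, 27, 33, 39, 45, then 57, 69, 81, 93: 10 doses through Week 45 and 14 through Week 104. SAP Table 1's three-weekly list matches the first ten exactly.

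**3. SAP Table 1, six-weekly list.** 0, 3, 6, 12, 18, 24, 30, 36, 42, 48, then 60, 72, 84, 96. Weeks in common: 0, 3 and 6. The other 10 − 3 = 7 doses through Week 45 (14 − 3 = 11 through Week 104) are each 3 weeks = 21 days from the nearest listed week. Footnote u offers a cross-check. Six-weekly pembrolizumab falls on multiples of 6. SNS-301 at 15, 21, ..., 45 never meets those weeks, as footnote u says; SNS-301 at 12, 18, ..., 48 always would.

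**4. Anticoagulant row, six-weekly schedule.**

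| | Weeks after Week 9 |
|---|---|
| SNS-301 doses | 15, 21, 27, 33, 39, 45, 57, 69, 81, 93 |
| Levels, Week 12 grid | (12), 18, 24, 30, 36, 42, 54, 66, 78, 90, 102 |

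Overlap is 0 of 6 to Week 45 and 0 of 10 to Week 104, whether or not Week 12 itself counts. Every dose is 21 days from the nearest level. Allowing 3 days on both visits closes at most 3 + 3 = 6 of those days. The alternative is to start at the first dose after Week 12, giving 15, 21, 27, 33 and 39: 5 of 6. That sequence steps from 39 to 45 and never lands on the row's stated Week 42, whereas 12 + 5 × 6 = 42 does.

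**5. Mixed texts.** The SNS-301 row's Week 9 mark and Week 45 end agree (9 + 36 = 45), but its Week 12 start does not (12 + 36 = 48). Section 3.2.3 likewise names Week 12 as the fourth dose but ends at 45 weeks. Each is internally inconsistent.

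**6. Three-weekly schedule and SAP Appendix A.** Here the anticoagulant row gives Week 12, then six-weekly to Week 45, then 12-weekly.

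- Counted forward from Week 12 it meets 0 of 6 (0 of 10 to Week 104) and never reaches Week 45.
- With Week 45 added as a check that restarts the 12-weekly count, it meets 1 of 6 (5 of 10).
- Counted back from Week 45 it meets 6 of 6 (10 of 10).

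SAP 8.7 goes six-weekly straight from Week 9 to Week 45 and meets 6 of 6 (10 of 10).

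**The case against.** The strongest reply is that this is editorial residue with little practical effect, and much of that stands.

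- **Dosing is directed elsewhere.** Protocol 7.1.2.3 tells sites to treat as described in 7.1.2.1, which is correct. Section 3.2.3 is rationale text. A reader might infer that it prescribes a rival Week 12 regimen, but it contradicts itself and does not govern dosing.
- **Footnote v.** A reader might infer that its Week 48 displaces doses. It displaces none in the six-weekly phase; only the start of the 12-weekly count is exposed.
- **Even-handed reading.** The SNS-301 row and the anticoagulant row open with the same Week 12 wording, so it is fair to ask why one is called mixed and the other a miss. The answer is the end week: 45 fits a Week 9 start, 42 fits a Week 12 start. The alternative for the anticoagulant row is possible but strained.
- **Safeguards.** Footnote i refers sites to the Concomitant Medications section. Levels are also drawn at any clinical bleeding, investigators are told to use routine anticoagulant tests, and SNS-301 is held for a clinically significant event. These reduce the risk but do not put a level on each dosing day.
- **SAP consequences.** A reader might infer that misplaced windows distort results. They do not: SAP section 4 uses no dosing window, and SAP 8.1 calculates exposure from actual first and last dose dates.
- **SAP 8.7.** A reader might infer that the end-of-treatment level is lost because 8.7 does not list it. SAP Appendix A marks a level at the discontinuation visit, so it is covered.

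**Conclusion.** The inconsistency is real and should be corrected, but it is a matter of schedule and safety monitoring and does not threaten the efficacy result.

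Two parts stand firmly. SAP Table 1 contradicts the regimen for six-weekly pembrolizumab at 7 of 10 doses through Week 45 (11 of 14 through Week 104) and lacks a six-weekly pembrolizumab window. The six-weekly anticoagulant row, on the reading that fits its own end week, meets none of the doses after Week 9 that 9.2.14.4 says must have a level. Footnote v's Week 48 is an arithmetic slip of limited reach, and 3.2.3 and the SNS-301 row need tidying.

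It would go too far to say that the three-weekly row and SAP Appendix A also miss the doses. Their wording allows anything from 0 of 6 to 6 of 6, so they are unclear rather than wrong.

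The counts are planned visits for a patient on six-weekly pembrolizumab throughout. The documents do not say how many patients take that option or how many of those use anticoagulants. Footnote u lets the investigator give a 200 mg dose to align visits, but that moves pembrolizumab, not the calendar weeks in the anticoagulant row.

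**What to change.** - Write the weeks explicitly (0, 3, 6, 9, 15, 21, 27, 33, 39, 45, then every 12 weeks from Week 45) in the six-weekly row of SAP Table 1, footnote v and the SNS-301 row of the six-weekly schedule, and protocol 3.2.3.
- Add the six-weekly pembrolizumab window to SAP Table 1.
- Change the anticoagulant row of the six-weekly schedule to each SNS-301 dosing visit plus the discontinuation visit. Clarify the three-weekly row and SAP Appendix A in the same way.
- State whether the Week 12 level is kept. Week 12 is not a dosing day, so the new wording would otherwise drop it without comment.
- Leave SAP 8.7 as it is, apart from a reference to Appendix A for the discontinuation-visit level.

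These are text edits and add no procedure beyond what 9.2.14.4 already requires. The SAP changes need a revised SAP. The protocol changes need IRB/IEC approval under 11.1.1 and can be carried in the next amendment.
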